**Anti-helminthic treatment:** Children >1 year of age will be given mebendazole, 100 mg two times daily for 3 days, if such treatment has not been provided in the last six months. This treatment will be provided after two weeks of nutritional rehabilitation.

**Follow-up:** After the child is discharged from the NRU, a health worker will visit the child every week for one month and then at fortnightly intervals until the child achieves an oedema-free WH >80%. During each visit, the child's general condition will be assessed, weight and height (or length) measured, presence or absence of oedema noted, supplies of micronutrients provided, compliance of feeding and micronutrient supplementation checked by 24 hours recall, and morbidity recorded, if any. To aid recall of morbid conditions, on each visit mothers will be given a pictorial calendar portraying a well child and children with diarrhoea, vomiting, cough, fever, eye infection, or discharging ears [10]. Mothers will be requested to record daily on the calendar whether the condition had been present or absent in the previous 24 hours. Morbidity will then be recorded on a precoded form with the help of the calendar. Diarrhoea will be defined as the passage of three or more watery or liquid stools per day. An episode will be considered new if at least two diarrhoea-free days intervene between the present and previous episodes. The health worker's identification of children with pneumonia of different grades of severity will be based upon WHO guidelines [11]. Lack of weight gain for two consecutive visits will constitute failure to respond. The health worker will refer to the CRSC any child with suspected serious illness, i.e., diarrhoea with some or severe dehydration, pneumonia, ear or throat infection, repeated episodes of fever, loss of appetite, or failure to respond to feeding. Self referral will also be encouraged and entertained at any hour of the day. The child will be evaluated and managed accordingly by any of the investigators (during day time) or the on-duty physician (at night). Readmission to the hospital and the NRU will depend upon existing CRSC guidelines. Any child readmitted to the NRU will not be re-enrolled into the study, but will maintain the pre-readmission status as a study subject. The physician will also record in the precoded form diagnosis, treatment, duration, and outcome of any severe illness including relapse of severe malnutrition or septicemia.

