### **Sample Size**

A preliminary analysis of 51 severely malnourished children (WH <70%) who received nutritional rehabilitation in our NRU after recovering from diarrhoea showed that the weight gain was  $8.4 \pm 7.3$  g/kg.day, and the time to achieve WH >80% was  $22.5 \pm 6.2$  days. In designing a trial with three or more groups, it is suggested that pair-wise comparisons between groups of central interest be first decided upon [13]. It is assumed that the proposed method of home-based nutritional rehabilitation with outpatient follow-up will result in a relatively lesser weight gain of 4 g/kg per day, will require approximately 35 days to achieve WH >80%, and lead to a 35% reduction in cost of treatment. Sample sizes of 58, 15, and 24 children in each group (hospital and home-based) were calculated from the assumptions of weight gain, time to achieve WH >80%, and reduction in cost of treatment respectively.

The formula used for calculating sample size is:

$$\frac{2 (SD)^2}{WD^2} \times \text{factor for } \alpha, \beta$$

where, SD is the standard deviation, WD is the worthwhile difference, power of detection is 90%, and type I error is 0.05. Taking the greatest of the three calculated sample sizes and allowing for 20% dropouts (refusal to continue, unexpected migration of the family to an outlying area, or later diagnosed to have tuberculosis), a sample size of 75 children in each group has been estimated.

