### **Outcome Measures**

- Time to recovery (achievement of WH 80%, oedema-free), in days
- Rate of weight gain, in g/kg per day calculated from lowest weight to discharge weight
- Speed of loss of oedema, in days
- Failure to respond
- Morbidity, in number and duration of episodes over equal periods of follow-up for both groups
- Mortality
- Cost of treatment

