## Data Analysis

Describe plans for data analysis. Indicate whether data will be analyzed by the investigators themselves or by other professionals. Specify what statistical softwares packages will be used and if the study is blinded, when the code will be opened. For clinical trials, indicate if interim data analysis will be required to monitor further progress of the study. (TYPE WITHIN THE PROVIDED SPACE).

Data will be analyzed using the SPSS Windows software. The Epi Info software will be used to calculate anthropometric indices. Enrollment characteristics will be compared between the three treatment groups. The outcome variables will be compared both within and between groups from enrollment to discharge. For normally distributed quantitative variables, means will be compared by ANOVA. Variables not normally distributed will be log transformed before analysis. Categorical variables will be compared by Chi-square test, multiple or logistic regression will be performed to minimise bias if required.

Results from all randomized children will be included in the analysis of the study. Data from children withdrawn because of failure to respond, TB, or voluntary dropout will be included in the analysis upto the time of withdrawal. A supplementary analysis excluding the children withdrawn may also be made.

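### The rule to log transform every non-normal variable cannot be applied to outcomes that can be zero, chiefly number and duration of illness episodes

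*Protocol*

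**What the plan says.** The Data Analysis section compares normally distributed quantitative variables by ANOVA and then sets one rule for all the others: "Variables not normally distributed will be log transformed before analysis". It names no added constant, rank test or count model. For categorical outcomes it states: "Categorical variables will be compared by Chi-square test".

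On who is analysed, the same section states: "Results from all randomized children will be included in the analysis of the study". It adds: "Data from children withdrawn because of failure to respond, TB, or voluntary dropout will be included in the analysis upto the time of withdrawal".

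Two entries under Outcome Measures are quantitative and can take the value zero:
- "Morbidity, in number and duration of episodes over equal periods of follow-up for both groups"
- "Rate of weight gain, in g/kg per day calculated from lowest weight to discharge weight"

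Failure to respond is listed there as a separate outcome. It is defined in the follow-up paragraph of Treatment A: "Lack of weight gain for two consecutive visits will constitute failure to respond".

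**The concern.** A child with no illness episode has a count of zero and a duration of zero. Neither has a logarithm, so the stated rule gives that child no value to analyse. Most software would return a missing value and leave the child out of the test without further notice. The morbidity comparison would then cover only children who fell ill. It would describe how much illness they had and ignore how many children in each arm stayed well. Staying well is part of what home and hospital care are being compared on, and selecting on it also breaks the randomized comparison.

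The same gap arises for weight gain, less often, when the last recorded weight is the lowest. The gain from lowest weight is then exactly zero.

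**Working it through.** **1. Which outcomes can be zero.** Enrollment requires that the acute illness has resolved (Enrollment Criteria; Management of Acute Illness), and hospital-arm children typically stay 15 to 25 days (Treatment C). A child with no new episode in such a period is an ordinary result. For weight gain, the numerator is final weight minus lowest weight. It is never negative, and it is zero only if the two coincide.

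**2. What the rule does at zero.** As x falls to 0, log(x) goes to minus infinity, so log(0) has no finite value. Applying the rule to all children and including all randomized children are therefore incompatible for any outcome with zeros.

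**3. Whether an added constant would rescue it.** With log(x + 1), every zero becomes log(1) = 0. If 37% of children have no episodes, 37% still share one value. A monotone transformation moves a spike but cannot spread it out, so the result is still not normal, and the answer now depends on the constant chosen.

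**4. How many children could be affected (morbidity).** The protocol gives no episode rate, so a range is assumed. For a Poisson count with mean m, the share with zero is exp(−m). With 75 per arm:

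| Assumed mean episodes per child | Share with zero | Children of 75 |
|---|---|---|
| 0.5 | exp(−0.5) = 61% | about 45 |
| 1 | exp(−1) = 37% | about 28 |
| 2 | exp(−2) = 14% | about 10 |
| 3 | exp(−3) = 5% | about 4 |

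If episodes cluster in some children, the share of zeros at a given mean is higher than the Poisson figure.

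**5. Whether weight gain falls under the rule.** Sample Size gives 8.4 ± 7.3 g/kg per day for hospital care, an SD-to-mean ratio of 7.3/8.4 = 0.87. A normal curve with these values puts Φ(−8.4/7.3) = Φ(−1.15) = 12.5% below zero. This suggests right skew if the figures were measured from the lowest weight, but Sample Size does not say that they were. The 12.5% is not an estimate of the share of zeros.

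**6. The scale on which the trial was sized.** Sample Size assumes that home care with outpatient follow-up "will result in a relatively lesser weight gain of 4 g/kg per day", a difference of 8.4 − 4 = 4.4. The protocol's formula with the usual factor of 10.5 (two-sided 0.05, 90% power) gives 2 × 7.3² / 4.4² × 10.5 = 57.8, hence the stated 58. That is a difference in arithmetic means. A test on logged values compares geometric means.

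**The case against.** The protocol nowhere tells the analyst to drop zeros, and its statement on the analysis set points the other way. A statistical analysis plan, which is not shown, could say how zeros are handled. This stands: exclusion is the likely consequence of an undefined value, not an instruction. But the rule is stated without exception, so such a plan would have to depart from it, and a constant would not cure the problem (step 3).

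The number of zeros may also be small. The follow-up paragraph of Treatment A tracks diarrhoea, vomiting, cough, fever, eye infection and discharging ears, and Budget Justifications refers to high morbidity. Means of 2 or 3, with 14% or 5% zeros, are as plausible as lower ones. This stands too, and is why the full range is shown.

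A reader might go further and infer that weight-gain failures as a class leave the comparison, narrowing the home-versus-hospital gap. The documents do not support that:
- Failure to respond means no gain at two consecutive visits. Such a child may have gained earlier in the nutritional rehabilitation unit and so have a positive rate from the lowest weight.
- A non-oedematous child enrolled below 70% weight-for-height who passes 80% must have gained weight. Zeros should arise mainly with early withdrawal or death, or while oedema is clearing.
- Children with oedema may enter at any weight-for-height. One could lose the oedema and meet the recovery criterion at the lowest weight: zero gain, yet a success. The direction of any bias is therefore not established.
- Failure to respond and mortality are categorical and stay in the chi-square comparison.
- No document gives the share of children with zero gain, so any figure for a narrowed gap would rest on invented inputs.

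Finally, logging a strictly positive, skewed outcome is standard practice. Preferring the original scale there is partly a trade-off, and the protocol is not wrong to allow logs for such variables.

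**Conclusion.** The concern holds for outcomes that can be zero. The log rule is undefined for them and cannot be carried out together with the commitment to include all randomized children. It matters most for number and duration of illness episodes. If undefined values become missing, between about 5% and 61% of children would leave the morbidity comparison, under assumed Poisson means from 3 down to 0.5 episodes per child. The protocol provides no rate with which to narrow that range.

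For weight gain the defect is the same in kind but occasional. It touches only children whose final weight is their lowest, and neither its size nor its direction can be derived from the documents. The wording should be corrected before analysis; the point does not call the design or the sample size into question.

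**What to change.** Replace the single sentence in Data Analysis with rules by type of outcome:
- **Log transformation:** only for strictly positive variables where a ratio of geometric means is wanted.
- **Number of episodes:** Poisson regression, or negative binomial if counts are overdispersed, with log child-days observed as offset. Withdrawn children contribute episodes and time up to withdrawal, which fits the protocol's own rule for them and allows for unequal observation.
- **Duration of illness:** days ill per day observed, compared by a method that keeps zeros, such as a rank test or bootstrap interval.
- **Rate of weight gain:** keep children with zero gain. Compare on the original scale, on which the 4.4 g/kg per day difference was sized, or use a rank test.

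The cost is one paragraph of wording and a little more analysis work. No new data are needed: illness and visits are already recorded on the precoded forms, and in the home-based arms also on the daily calendar.

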### Enrollment Criteria

Age:	6 months to 5 years
Gender:	Either
Nutritional status:	Severely malnourished (WH < 70% of the NCHS median or with oedema)
General condition:	Resolution of acute illness including diarrhoea, pneumonia, gross electrolyte imbalance, and septicemia. Criteria of resolution of acute illnesses are outlined under management of acute illness .
Place of residence:	Within 10 km from the CRSC (for convenience of follow-up)

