## Randomization

Randomization will be performed according to a random numbers table using permuted blocks of variable lengths.

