1. Children will be admitted to the nutritional rehabilitation unit (NRU) only upon resolution of acute illness(es) including diarrhoea, pneumonia, gross electrolyte imbalance, and septicemia. Criteria of resolution of acute illnesses have been defined in the protocol (attached herewith). Therefore, during the 7 days of stay in the NRU, the two groups of study children will be free of any acute illness that might pose a risk. However, if a child develops an acute illness during stay in the NRU or if the general condition is not satisfactory at the time of discharge, then the discharge will be postponed till resolution of the illness. This pre-condition to discharge is part of the management protocol.
2. In 41 severely malnourished children with bilateral pedal oedema consecutively admitted to our NRU for management, the median period of time taken for resolution of oedema was 7 days (mean  $\pm$  SD, 7.0  $\pm$  3.7 days). Therefore, by the time (by day 7 in our proposed study) children will be discharged from the NRU, most of them will be oedema-free.
3. In the oedematous form of protein-energy malnutrition, there is no simple association between mortality and the severity of weight loss, whereas the serum albumin concentration at admission is strongly associated with mortality (1). In a retrospective multivariate analysis seeking to find out the predictive markers of death in a cohort of 1129 children in Central Africa, serum albumin concentration, and not oedema, was found to be the best predictor of subsequent risk of dying (2). It was concluded from the study results that an isolated clinical sign such as oedema is not enough to detect severely malnourished children with a high risk of dying.

4. In a conceptually identical type of study done in Dhaka, the median period of time taken for resolution of oedema by severely malnourished children managed at home was 19 days, compared to 11 days by those managed on an inpatient basis (3). Mortality, however, was the same in both the groups, 3.5%.

In consistence with the pre-condition to discharge built within the study protocol and the literature cited, we feel that discharging some children with oedema after 7 days of NRU stay will not pose an additional risk. By the time the children are discharged, the mothers/caretakers will have learnt about proper care taking, feeding and identification of the acutely ill child.

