I would, therefore, request you to reconsider your decision about the inclusion criteria in our study, and allow us to enroll children with oedema who constitute one-third of all severely malnourished children admitted to the hospital (4).

Thanking you.

cc: Division Director  
Clinical Sciences Division

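### Whether to adjust for enrolment weight-for-height and oedema is left open until the data are seen; the main comparisons should adjust for both in any case

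*Protocol*

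**What the plan says.** The Data Analysis section has enrolment characteristics compared across the three arms, quantitative outcomes compared by ANOVA (after log transformation where not normal) and categorical outcomes by chi-square. It then adds that "multiple or logistic regression will be performed to minimise bias if required". It names neither a condition nor a covariate.

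On allocation, the Randomization section says only: "Randomization will be performed according to a random numbers table using permuted blocks of variable lengths". No stratification factor is mentioned.

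The Enrollment Criteria admit a child by either of two routes: "Severely malnourished (WH < 70% of the NCHS median or with oedema". The Outcome Measures define recovery as oedema-free WH 80% and list speed of loss of oedema, in days, as a separate outcome. Outcomes are compared from enrolment to discharge.

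The reply to the Ethical Review Committee, printed at the end of the protocol, argues for keeping oedematous children, described as "one-third of all severely malnourished children admitted to the hospital". Its point 2 reports 41 consecutive oedematous children in the nutritional rehabilitation unit (NRU), in whom "the median period of time taken for resolution of oedema was 7 days" (mean 7.0, SD 3.7). It concludes that by day 7 "most of them will be oedema-free", and later concedes that some children will be discharged with oedema.

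**The concern.** The conditional wording leaves two candidate main analyses for each outcome, one unadjusted and one adjusted, with no rule for choosing between them before results are known. The trial cannot be blinded, as the response to Reviewer 3 (point 4) accepts, so whoever makes the choice can know the allocation and the direction of the results.

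The choice matters because entry status is built into the endpoint. A child must climb from the enrolment WH to 80% and lose any oedema. The entry criteria also set no upper WH limit for an oedematous child, so for some children recovery may depend mainly on oedema loss. Variation in starting point that is left unmodelled goes into the error term.

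Two lesser matters follow from the same baseline variable. The day-7 statement to the ethics committee does not follow from the median beside it. And oedema loss is timed across a week in which all three arms receive the same care.

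**Working it through.** **1. The plan's own figure.** From the Sample Size section: SD 7.3 g/kg/day, difference 8.4 − 4 = 4.4, type I error 0.05 (two-sided reproduces the figure), power 90%. n = 2 × 7.3² / 4.4² × (1.960 + 1.282)² = 57.8, hence 58, as stated. With 20% dropout, 58 / 0.8 = 72.5, or 73; the stated 75 leaves 75 × 0.8 = 60 per arm.

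**2. How far starting WH moves time to recovery.** Assume constant height and constant gain at the protocol's 8.4 g/kg/day, with starting values of 60% and 69% chosen for illustration.
- From WH 60%: ln(80/60) / 0.0084 = 34.2 days (33% gain needed).
- From WH 69%: ln(80/69) / 0.0084 = 17.6 days (16% gain needed).

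The 16.6-day spread exceeds the 12.5-day difference assumed between arms (35 − 22.5). How strongly the same values predict the *rate* of gain is not given, so that enters below as an assumed R².

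**3. What adjustment buys for weight gain at 60 per arm.** Residual SD = 7.3 × √(1 − R²); power from the two-sample t-test.

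| R² (assumed) | SD | Power |
|---|---|---|
| 0 | 7.3 | 91% |
| 10% | 6.9 | 93% |
| 30% | 6.1 | 97% |

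The normal approximation gives values at most about one point higher.

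**4. Chance imbalance in oedema without stratification.** Oedematous children per arm are taken as three independent Binomial(75, p) counts. The share p among enrolled children is not stated, so a range is shown.

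| p (assumed) | Some two arms differ by ≥10 | One given pair differs by ≥10 |
|---|---|---|
| 20% | 13% | 5% |
| 25% | 17% | 7% |
| 33% | 23% | 10% |

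**5. Oedema at day 7.** By definition of the median, about 50% of oedematous children have cleared by day 7. A normal curve with mean 7.0 and SD 3.7 gives 45% at 6.5 days and 55% at 7.5 days. The reply does not give the count, but 21 of 41 would have an exact 95% interval of 35 to 67%. The reply also cites an 11-day inpatient median from another Dhaka study, which would put the share below half.

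Expected number in treatments A and B still oedematous at day 7, as 150 × share × 0.5:
- one-third: 25 (about 22 to 28 over the 45–55% range)
- one-quarter: about 19
- one-fifth: 15

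**6. Dilution of the oedema outcome.** At one-third there are 25 oedematous children per arm. About 12 or 13 lose their oedema during the shared NRU week, when the arms cannot yet differ. About 12 or 13 are left to show any contrast, or about 10 after 20% dropout. The Clinical Economics section itself places the start of differential costs at 7 days after randomization.

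**The case against.** The case against is substantial.

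- **Validity.** Unadjusted analysis of an unstratified randomized trial is valid. Chance imbalance is not bias, and omitting oedema as a stratification factor is not an error. A reader might infer that the comparisons are biased as written; the documents do not support that.
- **The trigger.** A reader might infer that baseline significance tests decide whether to adjust. The Data Analysis section places the baseline comparison and the regression in the same paragraph but does not link them. The criticism is that no rule is stated, not that this rule is.
- **Covariate list and model.** These are commonly left to a statistical analysis plan, which may exist, so their absence is no fault. The conditional wording is in the protocol and can be criticised.
- **Size.** Weight gain meets the planned 90% power unadjusted. For time to recovery the planning figures give 12.5 / (6.2 × √(2/60)) = 11 standard errors, so power is essentially 100%. Calculating weight gain from the lowest weight also limits distortion from oedema fluid. All this stands, and keeps the claimed gain modest.
- **One-third.** A reader might take it that one-third of trial children will have oedema. The reply gives that share for hospital admissions. Randomization follows acute care of roughly 4 to 7 days, during which some may lose it, so the enrolled share is unknown.
- **The day-7 statement.** It stands in a letter, not in the design, next to the median, mean and SD, and the letter concedes that some go home with oedema. Read as all discharged children it is even true: 1 − 1/3 × 1/2 = 83%. But the paragraph answers a concern about oedematous children, and for them it does not follow. It is not evidence that figures were withheld.
- **Starting the clock at day 7.** This selects on a post-randomization state, leaves few children, and day 7 is not a fixed divergence point because discharge can be postponed. This stands.

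**Conclusion.** The point holds as one about pre-specification and efficiency. The protocol leaves adjustment to a decision taken after the data are seen, in an unblinded trial, although two baseline values tied to the endpoint are available for every child. Always adjusting closes that choice. It raises power for weight gain from about 91% to 93–97% at 60 per arm if R² is 10 to 30%, a range the documents do not supply; with an R² near zero it gains and costs almost nothing.

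Stratifying by oedema is a reasonable option, not a correction. The chance that some two arms differ by 10 or more oedematous children is about 13–23% for an enrolled share of 20–33%.

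Secondary: about half, not most, of oedematous children should be clear by day 7. That leaves about 25 of 150 in A and B still oedematous if the admissions share carries over and days are counted from NRU entry. Speed of oedema loss from enrolment is diluted towards no difference, so a null result on it would be weak evidence that the arms are alike.

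**What to change.** - **Data Analysis.** Delete the condition. State that the main between-arm comparisons are adjusted for enrolment WH% and oedema (yes/no) whatever the baseline comparison shows: a linear model for weight gain, a time-to-event model for recovery, and a logistic model for failure to respond if events allow. Unadjusted results can be shown beside them. Cost: a few lines of text and no new data, since both covariates are needed to establish eligibility.
- **Randomization (optional).** Keep the permuted blocks but use separate lists for children with and without oedema. Cost: one extra list.
- **Reply to the ethics committee.** State that about half of oedematous children are expected to be oedema-free by day 7, and give the expected number in A and B still oedematous then (about 25 of 150) with the one-third assumption beside it. This corrects a figure and implies no change to any enrolment or discharge rule.
- **Speed of loss of oedema.** State that the first 7 days are common to all arms and that the comparison from enrolment is diluted. Label any analysis from day 7 as descriptive; it would rest on about 12 children per arm at best.

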## Clinical Economics

A complete, cost-benefit analysis from institutional as well as societal perspectives will be performed for all groups, starting from 7 days after randomization (point at which differential costs start). Cost of treatment to the CRSC will include capital and administrative costs, and expenses incurred for food, medicines, and laboratory tests. The cost of treatment to the parents will include expenses incurred for food, wage loss, transport and help needed at home during the mother's absence. This will be done in collaboration with the Health Economics Programme of ICDDR,B.

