## **Ethical Assurance for Protection of Human Rights**

Describe in the space provided the justifications for conducting this research in human subjects. If the study needs observations on sick individuals, provide sufficient reasons for using them. Indicate how subject's rights are protected and if there is any benefit or risk to each subject of the study.

This study will test the hypothesis that severely malnourished children recovering from diarrhoea, after an initial stabilisation period, can be rehabilitated nutritionally at home. As new drugs will not be tested, conduction of this study in human subjects is justified. After the acute phase treatment is over, the subjects in the study groups (home-based nutritional rehabilitation with follow-up at home or at the follow-up clinic) will be kept in the NRU for 7 days for stabilisation of general condition. Discharge from the NRU at the end of 7 days stay will be postponed if the general condition of a child is not stable. This will negate any risk to the subject.

After discharge at the end of 7-days stay in the NRU, the children will be visited at home or advised to attend the follow-up clinic at regular intervals. Any child failing to attend the follow-up clinic will be visited at his/her home. During the follow-ups at home or at the clinic, health and nutrition education will be reinforced, growth monitored, micronutrients provided, and the child referred to the CRSC if found to be ill.

The parents will always have the right to withdraw their children from the study at any time. Children withdrawn from the study will be provided with the conventional treatment at the CRSC. Mothers of children in the study group will not have to stay in the NRU for a prolonged period of time, which is an advantage for the families.

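### The protocol stops using data at withdrawal for failure to respond, which conflicts with its own follow-up rules and would leave later deaths and rescue costs uncounted in any arm

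*Protocol*

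**What the plan says.** The Data Analysis section first includes everyone: "Results from all randomized children will be included in the analysis of the study". The next sentence limits what is used: "Data from children withdrawn because of failure to respond, TB, or voluntary dropout will be included in the analysis upto the time of withdrawal". The one further analysis goes the same way: "A supplementary analysis excluding the children withdrawn may also be made". The rule is worded for all three arms.

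The follow-up text under Treatment A defines the event by visits: "Lack of weight gain for two consecutive visits will constitute failure to respond". It makes failure one of the grounds for referral to the CRSC, and then says: "Any child readmitted to the NRU will not be re-enrolled into the study, but will maintain the pre-readmission status as a study subject". On records it adds: "The physician will also record in the precoded form diagnosis, treatment, duration, and outcome of any severe illness including relapse of severe malnutrition or septicemia". Treatment B uses the same follow-up protocol.

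The section on Ethical Assurance for Protection of Human Rights says: "Children withdrawn from the study will be provided with the conventional treatment at the CRSC". Clinical Economics promises: "A complete, cost-benefit analysis from institutional as well as societal perspectives will be performed for all groups". It starts the count 7 days after randomization and lists cost components. It gives no end point and does not mention readmission or withdrawn children. Failure to respond, mortality and cost of treatment all appear under Outcome Measures.

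**The concern.** Failure to respond is one of the trial's outcomes. Using it to end a child's data means that one outcome decides whether two others, mortality and cost, are still observed. The children removed are those doing worst, so the truncation is informative.

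The second hypothesis is economic, and the Rationale makes cost-effectiveness the ground for extending the programme. When a home course fails and hospital care follows, that care is a cost of the home strategy. Mortality matters because the Ethical Review Committee's memorandum objected to sending oedematous children home after 7 days, and the reply relied partly on equal mortality of 3.5% in an earlier Dhaka study. If observation stops when a child fails, the trial's own answer on safety is weaker. An analysis plan written later cannot recover deaths or family costs that nobody collected.

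**Working it through.** **1. One child, two rules.** Take a home child with no weight gain at two successive visits who is then treated at the CRSC.

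| Question | Treatment A follow-up (also B) | Data Analysis |
|---|---|---|
| Does failure end participation? | No: referral, and a readmitted child stays a study subject | Yes: failure is a listed reason for withdrawal |
| Is what follows recorded? | Yes for severe illness: diagnosis, treatment, duration, outcome | Not used after withdrawal |
| Are family costs recorded? | Not mentioned | Not used after withdrawal |

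The Sample Size section counts refusal, migration and later-diagnosed tuberculosis as dropout, but not failure to respond. So the protocol's own lists of who leaves the study also differ.

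**2. Direction.** The rule covers all arms, so the bias depends on where failures occur. Two features point to the home arms. Sample Size assumes 4 g/kg per day and about 35 days for home care with outpatient follow-up, against 8.4 g/kg per day and 22.5 days in hospital. The failure definition is also tied to follow-up visits, and Treatment C does not explicitly carry it over to inpatients. Neither feature is a failure rate.

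**3. The plan's own figures.** The group size reproduces: 2 × 7.3² / 4.4² × 10.51 = 57.9, so 58, and 58 / 0.80 = 72.5, so 73, close to the stated 75. The 35% cost reduction cannot be reproduced, because no cost mean or standard deviation is given. It is taken below as the saving that would be reported if rescue costs were cut off.

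**4. Cost, as an illustration.** Set the counted hospital-arm cost at 1, so reported home cost is 0.65. Let f be the fraction of a home arm rescued after withdrawal and r the rescue cost relative to counted hospital cost. Both are assumptions.

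True home cost = 0.65 + f × r, so true saving = 0.35 − f × r.

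The top value of r supposes a full 22.5-day stay, against the 22.5 − 7 = 15.5 days counted for the hospital arm, with cost proportional to days: 22.5 / 15.5 = 1.45.

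| r | f = 5% | f = 10% | f = 20% | Saving gone at f = 0.35 / r |
|---|---|---|---|---|
| 0.5 | 32.5% | 30.0% | 25.0% | 70% |
| 1 | 30.0% | 25.0% | 15.0% | 35% |
| 1.45 | 27.7% | 20.5% | 6.0% | 24% |

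This charges each failing child a whole home course plus the rescue. If failing children instead used half a home course, then at f = 20% and r = 1 the reported cost is 0.65 × 0.8 + 0.325 × 0.2 = 0.585 and the true cost is 0.785. The true saving is 21.5% and the break-even is 0.35 / 0.675 = 52%. The gap between reported and true stays at f × r = 20 points.

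If failures and rescue costs were equal in all arms, the absolute difference would stay at 0.35. At f = 10% and r = 1 the percentage saving would then move only from 35% to 0.35 / 1.10 = 31.8%.

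**5. Mortality.** At 3.5%, an arm of 75 expects 75 × 0.035 = 2.6 deaths. Each death left out lowers that arm's rate by 1/75 = 1.33 percentage points.

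**The case against.** A reader might infer that the protocol charges the rescue of home failures to no arm and leaves their deaths out of the home arms. The documents do not support that.

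- **The Treatment A text points the other way.** A failing child is referred, a readmitted child remains a study subject, and treatment and outcome of severe illness are recorded. Such a child can still be counted. This stands, and it turns the point into a conflict between sections. It does not remove the Data Analysis rule, which names the same event as a reason for withdrawal.
- **Clinical Economics is a separate section and excludes nothing.** Applying the withdrawal rule to costs is an inference. That also stands. But the section states no rule of its own for withdrawn children, so nothing in it overrides the Data Analysis sentence.
- **The sentence on conventional treatment follows one about parents' right to withdraw.** It may be meant only for them. Its wording is general, however, and failures are in any case referred to the CRSC.
- **The rule covers every arm.** The Background reports high dropout and mothers unwilling to stay long in the NRU, so truncation may also remove hospital-arm cost. This stands: the direction is plausible, not established. Tuberculosis withdrawals in particular need not differ by arm.
- **The figures are assumed.** Neither the failure rate nor the rescue cost is in the documents, and the main formula takes the costly case for each failure. This stands, so the table is an illustration only.

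**Conclusion.** The point holds in a limited form. The protocol contradicts itself on whether failure to respond ends participation. If the Data Analysis sentence is followed, later deaths and rescue costs of withdrawn children are not counted in any arm, and the supplementary analysis goes further by removing those children altogether. The cost and mortality comparisons would then favour whichever arm has more failures. The home arms are the likelier candidates, given the slower gain assumed for home care and the visit-based definition, but no rate by arm is given.

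The size of the bias cannot be derived from the documents. With 5% to 20% of a home arm rescued at 0.5 to 1.45 times counted hospital cost, the planned 35% saving would be about 32.5% down to 6%. That range rests on the assumed values of f and r, on reading 35% as the saving before any rescue cost, and on no offsetting loss in the hospital arm.

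**What to change.** Reconcile the Treatment A follow-up text, Data Analysis, Clinical Economics and the Ethical Assurance section. Whether failure ends the assigned regimen is for the investigators to settle. The statistical requirement is that it should not end data collection. Replace the Data Analysis sentence on withdrawn children along these lines:

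> Stopping the assigned regimen for failure to respond or tuberculosis does not end data collection. For every randomized child in all three arms, vital status, weight, oedema, and costs to the CRSC and the family, including any readmission, are collected to a common, defined end point and counted in the arm assigned. Collection stops early only where parents refuse further contact. Failure to respond is analysed as an outcome.

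State the same end point in Clinical Economics, with a sentence that costs after stopping the regimen or after readmission count in the assigned arm.

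The cost is modest. Hospital records are already a study source (Abstract Summary for the Ethical Review Committee, item 8), and follow-up staff are in the budget. The downside is some extra recording, including wage loss, transport and home help, which hospital records do not hold, and a home-care saving that may look less favourable. The change should be made before enrolment, because follow-up that was not done cannot be reconstructed.
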